postpartum than are those who describe themselves as very confident²⁹. Self-efficacy is a dynamic process throughout the postpartum period, especially during vulnerable cessation periods³⁰. Low maternal confidence has been associated with the perception of inadequate milk supply and is related to early discontinuation of breast-feeding, especially during the first 2 weeks³⁰. Only one descriptive study (n=172) was found on the use of technology to assess breast-feeding knowledge of childbearing families³¹. Lack of knowledge was found related to milk supply and to pumping in special circumstances³¹. Specific individualized interventions, especially during the initial critical 2-6 week period, are needed to prevent deterioration in intention levels for breast-feeding for 6 months and breast-feeding self-efficacy levels within the first 2 weeks postpartum which could lead to the decision to discontinue breast-feeding³¹.

A prior study showed significant improvement in the knowledge gained about the chronic illness self management among rural women using computer based health education³². Increase in human immunodeficiency virus (HIV)/acquired immune deficiency syndrome (AIDS) knowledge and self-efficacy was seen when intent to treat model was implemented using internet. The study demonstrated the acceptability and efficacy of the internet for delivering HIV prevention messages to rural men who have sex with men³³.

The objective of the proposed study is to explore acceptance of bilingual, interactive touch screen computer based breast-feeding educational program and also explore its effect on improving breast-feeding knowledge, breast-feeding self-efficacy and partial to exclusive breast-feeding among pregnant Hispanic rural women.

Significance

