The subjects will be enrolled at RWMC, Scottsbluff and randomly assigned to either intervention (bilingual Computer based Breast-feeding Educational Support program) or attention control (bilingual breast-feeding printed educational material) groups during the subject's prenatal visit (i.e. anytime during last six weeks of their pregnancy). Once randomized, baseline information will be gathered in both the groups as outlined in Figure5. The difference between the two study groups is that subjects in the intervention (bilingual Computer based Breast-feeding Educational Support program) will record their baseline assessment on a computer and receive tailored breast-feeding education compared to the attention control (bilingual printed breast-feeding educational materials) who will record their baseline information on paper (Figure5) and receive printed breast-feeding educational material. Using self report responses of the individuals in the intervention group (bilingual computer based breast-feeding educational support program), the decision logic and algorithm will process the information and deliver tailored breast-feeding educational messages in varied multimedia formats using a combination of text, images, and animations to account for the literacy levels of the subjects. Appropriate feedback will be given in the form of reinforced educational messages and encouragement and motivational prompts for those using the computer based program. Educational session in both the groups will last for 30 minutes. The first educational session will be performed during the post partum period, one day before the discharge from the hospital followed by week 6, months 3 and 6. Specific individualized interventions, especially during the initial critical 2-6 week period, are needed to prevent deterioration in intention levels for breast-feeding for 6 months and breast-feeding self-efficacy levels within the first 2 weeks postpartum which could lead to the decision to discontinue breast-feeding³¹. Subjects in both the groups will be given telephone reminders for follow up educational sessions. The touch screen computer based Breast-feeding Educational Support program will be placed on a mobile cart in the outpatient clinic of the RWMC, Scottsbluff. A research assistant will be available to guide the subjects in both the intervention (during the use of the tablet pc program) and the control groups (printed educational material) if needed. The breast-feeding educational modules and data collection instruments will be both in English and Spanish.

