Acceptance of Computer-based Breast-feeding Educational Support program: We will adapt and use previously published questionnaire used to assess acceptance of computer based asthma educational program⁴⁶ (Appendix F). Feedback will be gathered on ease of use of program, navigation patterns, and feedback during the program, future use of program and recommendation to others to use the program. Usage data analysis will help to understand learning patterns during use of the computer program by gathering the amount of time an individual spent on viewing the educational modules.

d. Potential Confounders

Socio-demographics: Include age, income levels, employment status, and education level, smoking status, prior pregnancies and previous history of breast-feeding. Information is also gathered about prior use of computers, its frequency of usage prior use of internet and sources of health information (Appendix G). Health literacy is the ability to perform basic reading and numerical tasks required to function in the health care environment⁶⁵. Studies have shown an association between limited health literacy and worse health outcomes such as poorer knowledge about health conditions^{66, 67}. The 3 health literacy screening questions, which performed optimally in a previous study⁶⁸, will be used to assess health literacy assessments of Hispanic rural women (Appendix H) and include: "How often do you have someone (like a family member, friend, hospital/clinic worker or caregiver) help you read hospital materials?" (Help Read), "How often do you have problems learning about your medical condition because of difficulty understanding written information?" (Problems Reading), and "How confident are you filling out forms by yourself?" (Confident with forms). Responses will be scored on a Likert scale from 0 to 4 and were asked to choose between all of the time, most of the time, some of the time, a little of the time or none of the time⁶⁸.

In addition, Newest Vital Sign (NVS) consisting of a nutrition label with 6 accompanying questions to assess literacy will be used⁶⁹. It takes approximately 3 minutes to administer, and is meant to allow healthcare providers to make a quick assessment of patients' literacy, which can then allow them to adapt communication to achieve better outcomes. It assesses literacy and numeracy, and is available in both English and Spanish versions. The

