Baseline data will be gathered during the enrollment prenatal visit (anytime during last six weeks of pregnancy) and follow up data will be collected on postpartum day 3, week 6 and months 3 and 6 resulting in overall five data collection time periods. The postpartum day 3 data collection will be done over the telephone while other follow up data collection including week6 and months 3 and 6 will be done when the individuals in both the groups will come to the hospital for follow up educational sessions. Almost all women who initiate breast-feeding plan to continue for at least 6 weeks; however, one of every five women quits breast-feeding within the first days after delivery⁷³. This finding supports the notion that 2–4 weeks postpartum is a vulnerable period for breast- feeding cessation⁷⁴. Baseline evaluation will be done during the prenatal visit (last trimester). The research assistant will schedule a follow up interview to administer the study questionnaires at a convenient time over the telephone. Subjects will receive gift vouchers worth \$15 for baseline and for every follow up postpartum visit (Table2).

Pre and Post educational Session data collection	Baseline	Day 3	Week 6	Month 3	Month 6
Socio-demographics	X				
Health Literacy	X				
Breast-feeding Knowledge	X	X	X	X	X
Breast-feeding self-efficacy	X	X	X	X	X
Intent to Breast-feed	X	X	X	X	X
Breast-feeding attitudes	X	X	X	X	X
Perceived norms	X	X	X	X	X
Program acceptance	X				X

Table2. Data Collection in intervention and attention control groups

Informed Consent

[name] (Consultant) is a bilingual and certified Spanish translator and will administer the informed consent and assent forms at the RWMC, Scottsbluff after the eligible subjects have agreed to participate in the study. The research staff members will read the UNMC IRB-approved consent and assent forms to subjects describing the study, the measures used by the researchers to protect the confidentiality of the responses, and the voluntary nature of the study. Those who agree to participate will be asked to sign the consent and the assent forms as appropriate. The research staff member will countersign the consent and the assent forms and copies will be given to the participant.

Data Entry and Quality Assurance

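### The acceptance questionnaire is scheduled before the first stated educational session and then only at month 6, so every post-session rating comes from women still attending at month 6

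*Combined protocol and SAP*

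**What the plan says.** The objective at the end of I. Background and Significance opens with acceptance: "The objective of the proposed study is to explore acceptance of bilingual, interactive touch screen computer based breast-feeding educational program". Under Dependent Variables, the acceptance questionnaire is described by content: "Feedback will be gathered on ease of use of program, navigation patterns", followed by feedback given during the program, future use and recommendation to others. The same paragraph adds usage data, namely time spent viewing the modules.

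Under Data Collection procedures, Table 2 has a row "Program acceptance" with marks at baseline and month 6, and none at day 3, week 6 or month 3. The five rows for knowledge, self-efficacy, intent, attitudes and norms are marked at all five time points. The table's caption, "Table2. Data Collection in intervention and attention control groups", covers both arms and its header reads "Pre and Post educational Session data collection", without saying which marks are pre-session and which are post-session.

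On timing, the same section says "Baseline data will be gathered during the enrollment prenatal visit (anytime during last six weeks of pregnancy", while IV. Research Design and Methods says "The first educational session will be performed during the post partum period, one day before the discharge from the hospital", with later sessions at week 6, month 3 and month 6. Day-3 data are collected by telephone. Week-6, month-3 and month-6 data are collected when women come to the hospital for those sessions.

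**The concern.** The questionnaire items presuppose use of the program. Read against the session schedule, the first of the two acceptance marks falls before any scheduled session, and the second falls at the last one. A woman who has a session at discharge, week 6 or month 3 and then stops coming has no scheduled occasion to rate what she used.

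The trial's title asks about feasibility, and the pilot is meant to lay the ground for a larger multicentre randomised trial. An acceptance figure drawn only from women retained to month 6 would carry into that planning. If dislike of the program is one reason for leaving, the figure is too high, and the data collected would not show by how much.

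**Working it through.** **Order of events, from the text**

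| Time | Educational session (IV. Research Design and Methods) | Acceptance questionnaire (Table 2) |
|---|---|---|
| Prenatal visit, last six weeks of pregnancy | none stated; intervention arm enters baseline data on the computer | X |
| One day before discharge | first session | – |
| Day 3 (telephone) | – | – |
| Week 6 | session | – |
| Month 3 | session | – |
| Month 6 | session | X |

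There are four sessions. No rating is scheduled after any of the first three until the month-6 visit.

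**What baseline can measure.** Intervention women record their baseline assessment on the computer, and the description of the tool under Conceptual framework counts screening questions as one of its three components. They could therefore rate some ease of use. They could not rate educational sessions that have not yet taken place. Control women receive printed material and have no program to rate at either mark.

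**Size.** The documents give no acceptance rate and no precision target for acceptance, so there is no figure of the plan's own to reproduce on this point. The inputs from Sample Size Justification are 27 women per group and 15% attrition.

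- Expected responders at month 6: 27 × (1 − 0.15) = 22.95, about 23. Lost: 27 − 23 = 4.
- Assume 20 of the 23 responders accept: 20/23 = 87.0%, exact (Clopper-Pearson) 95% CI 66% to 97%.
- If none of the four lost would have accepted: 20/27 = 74.1%, exact 95% CI 54% to 89%.
- If all four would have accepted: (20 + 4)/27 = 24/27 = 88.9%, exact 95% CI 71% to 98%.

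The reported 87% could thus exceed the figure for all 27 by up to 87.0 − 74.1 = 12.9 points, or fall short of it by up to 88.9 − 87.0 = 1.9 points.

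**Sensitivity to the assumptions**

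| Attrition | Responders | Accept (assumed) | Among responders | Range among all 27 |
|---|---|---|---|---|
| 15% (plan) | 23 | 18 | 78% | 18/27 = 67% to 22/27 = 81% |
| 15% (plan) | 23 | 20 | 87% | 20/27 = 74% to 24/27 = 89% |
| 15% (plan) | 23 | 21 | 91% | 21/27 = 78% to 25/27 = 93% |
| 25% (assumed) | 20 | 18 | 90% | 18/27 = 67% to 25/27 = 93% |
| 35% (assumed) | 18 | 16 | 89% | 16/27 = 59% to 25/27 = 93% |

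When most responders accept, the possible error is larger in the direction of overstatement, and it grows with attrition.

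**Analysis.** Table 3 has no row for program acceptance, so neither the denominator nor the handling of missing ratings is defined.

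**The case against.** Several points on the other side have force.

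- **Prenatal exposure may have been intended.** The sentence in IV. Research Design and Methods on baseline recording also mentions receiving tailored education, the Analysis Plan speaks of informing subjects during the prenatal visit, and the Table 2 header refers to pre- and post-session data. Figure 5, which might settle the matter, is not available in the text reviewed. This stands: the only explicit schedule is postpartum, but removing the baseline mark should wait until the sections are reconciled.
- **Baseline is not empty.** A reader might infer that women have nothing to rate at baseline and that the reading is worthless in both arms. The documents do not support that for the intervention arm, which has already entered data on the computer.
- **Bias is not shown.** A reader might also infer that acceptance is biased upward by 13 points. Nothing in the documents says that women leave because they dislike the program, and 13 points is only the worst end of a range built on an assumed 20 of 23.
- **Other data exist.** Usage logs are recorded at each use, so women who leave after a session still contribute. That stands for viewing behaviour, but logs do not record willingness to reuse or recommend the program.
- **Telephone follow-up is possible.** Telephone contact is an eligibility criterion, and a telephone interview for study questionnaires is mentioned, so it cannot be said that women who leave will never be asked. However, acceptance is not assigned to that call.
- **An end-of-program rating is a legitimate choice.** Month 6 is itself a session visit, so the rating need not rest on distant recall. This supports keeping month 6; it does not supply ratings from those who left earlier.
- **The two-arm reading rests on a shared caption.** The questionnaire is named as one about the computer program, so this part is a matter of table wording.

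**Conclusion.** The point holds in limited form. As scheduled, the acceptance questionnaire comes once before the first explicitly scheduled session, when it can capture at most the intervention arm's data-entry experience, and once at month 6 among women still attending. Upward bias is plausible but conditional on dislike contributing to drop-out. With the plan's 15% attrition and an assumed 87% acceptance among 23 responders, the value among all 27 lies between 74% and 89%.

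That illustration uses all 27 women randomised to the intervention arm. Randomisation is prenatal and several exclusions can arise only at or after birth, so some of the four lost may never have had a session. The range among women with at least one session could then be narrower.

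The primary outcome is unaffected. This is a cheap improvement to the measurement of a headline objective.

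**What to change.** 1. In Table 2, add an acceptance mark for the intervention arm at the first existing data contact after the woman's first session: the day-3 call, or week 6 if that session has not yet happened by day 3. Keep month 6.
2. Collect the rating by telephone from women who stop attending.
3. Limit the acceptance row to the intervention arm.
4. Add a Table 3 row for acceptance. Report it among all intervention women with at least one session, with an exact 95% CI and best- and worst-case bounds for missing ratings.
5. Reconcile IV. Research Design and Methods, the acceptance paragraph under Dependent Variables, and Table 2 on when the program is first used. Remove the baseline mark if no educational exposure occurs at the prenatal visit. If one does occur, say so and state that the rating follows it.

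The cost is a few more minutes at an existing call or visit, telephone calls to the few women who stop attending, and edits to two tables. No new visit or instrument is needed.

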
[figure not shown]

Figure5. Flow chart and education sessions in intervention and attention control groups

Description of the variables

The relevant study variables include (i) independent variables, (ii) process variables, (iii) potential confounding variables and (iv) dependent variables (outcomes). All the data gathering instruments will be available both in English and Spanish.

a. Independent variables

The study will have two groups: intervention group will receive bilingual Computer based Breast-feeding Educational Support program while attention control group will receive bilingual printed breast-feeding educational materials

b. Process variables

Variables impacting breast-feeding duration include;

Breast-feeding Knowledge: The Breast-feeding Questionnaire (BKQ)²⁴ was used in a randomized clinical trial of education and support for adolescent mothers²⁴. Items from two tests of breast-feeding knowledge^{55, 56}, were combined to provide a 30-item measure. Nineteen items developed for use with adolescent girls as a measure of laypersons' breast-feeding knowledge⁵⁵, were used in combination with 11 items from the Breast-feeding Knowledge Questionnaire (BKQ) ⁵⁶. The questionnaire includes multiple-choice and true-false items on the components of breast milk, colostrums, weaning and breast-feeding techniques. Reliability (internal consistency alpha coefficient-KR20) of the measure was .70 (Appendix B).

Breast-feeding Attitude/Beliefs: The Breast-feeding Attrition Prediction Scale (short-form) [BAPT] Spanish and English^{38, 39}. This 35 item scale is based on theory of planned behavior⁵⁷. It includes 4 sub-scales:1) positive breast-feeding sentiment (PBS); 2) negative breast-feeding sentiment (NBS); 3) social support and professional support (SPS) and 4) perceived behavioral control (PBC) for breast-feeding. Two International Board Certified lactation consultants reviewed the revised BAPT and judged the items to be both relevant and appropriate. Reliability was good with sub-scales scoring .67-.88 Cronbach's alpha. The overall scale demonstrated predictive validity by differentiating sustained breast-feeding at 8 weeks ³⁸ (Appendix C)

Perceived norms: Is described as the perceived pressure to perform a behavior³⁴. Social pressure will also be measured by a sub-scale of the revised BAPT. It is critical that perceived norms be measured for Hispanic

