mothers since familism is an important cultural social structure in which the needs of the family as a group are more important than the needs of any individual family member and may include nutrition behaviors⁵⁸. This strong cultural value in Mexican American families embodies social support within the extended family^{59, 60} (Appendix C)

Breast-feeding Self-Efficacy: Self-efficacy is the personal belief that one can effectively perform a given behavior and that the behavior will result in the desired outcome. Self-efficacy has also been identified as a modifiable psychosocial variable in predicting behavior performance⁶¹, including sustained breast-feeding⁶². We will use Breast-feeding self-efficacy scale short form (BSES-SF). The BSES-SF is a 14-item 5-point Likert scale questionnaire that has response categories that range from 1 = not at all confident to 5 = always confident. An internal consistency alpha coefficient of .97 was obtained for the revised total scale. Predictive validity was demonstrated by significantly higher breast-feeding self-efficacy scores in breast-feeding mothers compared to bottle-feeding mothers at 4 ($p < .001$) and 8 ($p < .001$) weeks postpartum. Content validity of 86% was established with a review by an expert panel⁶² (Appendix D)

Intent to breastfeed for 6 months: -is defined as readiness to engage in a behavior. It will be measured by an intention question related to the mother's perceived intent to breastfeed for the recommended 6 months. The question has been developed based on Fishbein & Ajzen's guidelines³⁴ and is "How likely is that you intend to breastfeed for 6 months is measured by a 7 point Likert scale (extremely likely to extremely unlikely)?"

c. Dependent Variables

Primary outcome: Primary outcome is partial (combined formula and breast milk feeding) or exclusive breast-feeding at six months⁶³ and will be assessed using breast-feeding assessment questionnaire⁶⁴ (Appendix E). The questionnaire will also assess information about the timing of introducing solid food during the first six months. Exploratory analysis will also be performed to determine the proportion of Hispanic rural women who continue to do exclusive breast-feeding at six months in both the intervention (bilingual computer based breast- feeding educational support program) and control (bilingual printed breast-feeding educational materials)

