In the first step of exploratory analysis, we will present a table to summarize the distribution of all variables, including outcomes, confounding, and process variables. This table will also serve the purpose of quality control of the original data, to mine missing data patterns and outliers. The distributions of the continuous outcomes will be explored for normality and transformations will be used if warranted. Continuous variables will be summarized using means, medians, standard deviations and ranges while categorical variables will be examined using frequencies and percentages. Exploratory analysis on process variables will be used for post-hoc analysis. Inter-rater reliability of knowledge, attitudes/beliefs, self-efficacy and intent to breast feed will be examined using the kappa statistic.

Sample Size Justification

The optimum number of participants for a focus group is typically 6-10 people with similar backgrounds who participate in the interview for one to two hours may vary⁵². The number generally suggested as being manageable is between six and ten participants as smaller groups show greater potential and large enough to gain a variety of perspectives and small enough not to become disorderly or fragmented⁵². For the intervention effect analysis, a comparison of two independent binomial proportions using Pearson's Chi-square statistic with a two-sided significance level of 0.05, a sample size of 23 per group achieves a power of at least 0.8 when the proportion with partial breast-feeding at 6 months are 0.3 for the control group and 0.7 for the intervention group. To account for anticipated attrition of 15%, the sample size will be increased to 54 subjects (27 per group). This is a pilot study to explore the possibility of promoting breast-feeding using computer based breast-feeding tailored educational program among Hispanic rural women.

Statistical Analysis

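### Inter-rater kappa is planned for self-reported scales for which no second rating is described, so the only in-sample reliability check planned for them has no data

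*Combined protocol and SAP*

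**What the plan says.** The Exploratory Data Analysis section (VII. Analysis Plan) commits to one reliability analysis: "Inter-rater reliability of knowledge, attitudes/beliefs, self-efficacy and intent to breast feed will be examined using the kappa statistic".

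The research design section (IV) describes where the answers come from. Women in the intervention group "will record their baseline assessment on a computer and receive tailored breast-feeding education"; the controls are those "who will record their baseline information on paper". The tailoring algorithm is driven by the woman's own answers: "Using self report responses of the individuals in the intervention group". Under Data Collection procedures, "The postpartum day 3 data collection will be done over the telephone", and a staff role is mentioned: "The research assistant will schedule a follow up interview to administer the study questionnaires at a convenient time over the telephone".

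Elsewhere, reliability appears only as coefficients from earlier use of the instruments, under Process variables. For knowledge: "Reliability (internal consistency alpha coefficient-KR20) of the measure was .70". For self-efficacy: "An internal consistency alpha coefficient of .97 was obtained for the revised total scale". For the BAPT sub-scales, Cronbach's alpha of .67 to .88 is cited.

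**The concern.** An inter-rater statistic measures how far two or more raters agree when they classify the same thing. Here the thing measured is what the mother knows, believes, feels confident about or intends, and she is its only source. If nobody rates the same answers a second time, there is no agreement table and no kappa.

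What is at stake is the reliability check itself. The pilot aims to improve knowledge and self-efficacy, compares both by t-test, and is meant to prepare a larger multicenter trial. Whether the instruments hold together in this population is something it should be able to report. The documents give earlier coefficients but plan no alpha, KR-20, intraclass correlation or test-retest in this sample. If the kappa sentence yields nothing, no in-sample evidence remains for these scales.

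**Working it through.** This is mainly a matter of reading the measurement sections against the analysis sentence. The plan states no kappa target, number of raters or sample size for reliability, so it has no reliability figure to reproduce.

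**Step 1. What each measure is, and who supplies the rating.**

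| Measure | Format (Process variables) | Source of the answer | Second rating described? |
|---|---|---|---|
| Knowledge | 30 items, multiple choice and true-false | Mother | No |
| Attitudes/beliefs (BAPT) | 35 items, 4 sub-scales | Mother | No |
| Self-efficacy (BSES-SF) | 14 items, 5-point | Mother | No |
| Intent | 1 item, 7-point | Mother | No |

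**Step 2. Could a second rating come from elsewhere in the plan?**
- *Telephone contact and staff help.* An assistant who reads out questions records the mother's answer and does not form a separate judgement. No duplicate interview is described.
- *Data entry.* The Data Entry and Quality Assurance section describes automatic inconsistency checks against the original forms. It does not describe two people entering the same form.
- *Repeated visits.* Table 2 schedules these scales at baseline, day 3, week 6 and months 3 and 6. These are repeated measures around an intervention meant to change the scores, not two ratings of the same state.

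None of these gives paired ratings.

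**Step 3. What could be estimated instead, and how precisely.** Inputs: the cited KR-20 of .70 with 30 items, the cited alpha of .97 with 14 items, and the planned 54 women (23 × 1.15 = 26.45, rounded up to 27 per group; 2 × 27 = 54). Two assumptions are made: the cited coefficients hold in this sample, and all 54 complete baseline. The language split is not in the documents, so 27 and 14 women in one language are shown as a range.

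Feldt 95% interval: lower = 1 − (1 − α)·F(0.975), upper = 1 − (1 − α)·F(0.025), with n − 1 and (n − 1)(k − 1) degrees of freedom, where k is the number of items.

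| Scale | n | df | F(0.025), F(0.975) | 95% CI |
|---|---|---|---|---|
| Knowledge, .70, k = 30 | 54 | 53, 1537 | 0.6527, 1.4262 | 0.57 to 0.80 |
| Knowledge | 27 (assumed) | 26, 754 | 0.5289, 1.6316 | 0.51 to 0.84 |
| Knowledge | 14 (assumed) | 13, 377 | 0.3823, 1.9376 | 0.42 to 0.89 |
| Self-efficacy, .97, k = 14 | 54 | 53, 689 | 0.6486, 1.4396 | 0.957 to 0.981 |
| Self-efficacy | 27 (assumed) | 26, 338 | 0.5247, 1.6552 | 0.950 to 0.984 |

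Example, first row: 1 − 0.30 × 1.4262 = 0.572 and 1 − 0.30 × 0.6527 = 0.804. No interval is given for the BAPT sub-scales because the documents do not state how many items each contains.

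The pooled estimate is usable. For knowledge, the estimate by language is loose.

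**The case against.** The strongest reply is that the case rests on silence. The study manual and the instrument appendices are not in view, several research assistants are involved, and not every administration is self-completed. The heading of Table 2 also speaks of data collection before and after the educational session, which can be read as two administrations at one visit. So it is too strong to say that the analysis could never be run. What stands is narrower: nothing in the documents supplies a second rating, and even two administrations to the same woman would be test-retest data, not inter-rater data. If some other form of agreement was meant, the sentence still has to be rewritten to say so.

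Three stronger readings are tempting, and the documents do not support them.
- *Kappa is the wrong type of statistic because the scores are continuous.* Table 3 treats knowledge and self-efficacy as continuous, but lists intent as categorical and attitudes as both, and individual items are categorical. The missing second rating is the objection; the data type is secondary.
- *All the scales are newly combined or adapted and therefore unchecked.* Only the BAPT items are described as adapted for the computer program (Conceptual framework). The 30-item knowledge measure was combined for an earlier trial, and the .70 is presented as the reliability of that measure. The self-efficacy scale is an existing short form. For those two, the gap is only that no in-sample or Spanish-specific coefficient is given.
- *The error costs the t-tests power.* Imperfect reliability does weaken a comparison, but by the same amount whichever coefficient is reported. Replacing kappa with alpha changes no test's power.

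It is also fair to say that the plan never promises internal consistency, so proposing it goes beyond correcting an error. It is, however, the form of reliability that the protocol itself cites for these scales, and it uses item responses that the study collects anyway.

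**Conclusion.** The point holds in limited form. The plan names an inter-rater analysis for four self-reported measures and describes no second rating, so its only in-sample reliability check for them has no data to work on. This follows from the text and needs no numerical assumption, except that the unseen manual and appendices add no second rater.

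The severity is minor. The sentence sits under exploratory analysis and concerns process variables. The loss is a reliability estimate that a pilot preparing a larger trial should want, most clearly for the adapted BAPT items. The precision figures assume that the cited coefficients carry over to this sample, and the figures by language also assume a split that the documents do not give.

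**What to change.** Replace the kappa sentence with wording such as: Internal consistency at baseline will be reported as KR-20 for the 30-item knowledge score and as Cronbach's alpha for each BAPT sub-scale and for the BSES-SF, with 95% confidence intervals for the whole sample and, descriptively only, by language version.

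Leave the single intent item out, because internal consistency is not defined for one item; its reliability would need a repeat administration. Keep kappa only for material that two people actually code, for example focus-group transcripts if two analysts index them independently.

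The cost is one sentence in the analysis plan and a few lines of code on item-level baseline responses. It adds no visits, questionnaires or participants, and leaves the sample size and the primary analysis unchanged.
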